16.2.8 Chart Review of Abscopal Effect

Summary statistics (counts, percentage, mean, standard deviation, etc.) will be presented for exploratory endpoint as appropriate. Statistical comparison of the number of non-melanoma skin cancers in the 12 month and 24 month period prior to the TVEC injections versus the number in the 12 months after the TVEC injections will be performed using the Wilcoxon Rank Sum Test.

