6.1 Inclusion Criteria

- a. Able to give informed consent in English or Spanish
- b. Age > 18
- c. Have at least one >0.5 cm to <5.0 cm, histologically confirmed low risk cutaneous SCC (including kerathoacanthomas)
- Size >0.5 cm on trunk or extremities (excluding face, neck feet, nail units, and ankles)
- Clinically consistent with primary tumors.
- Lesion considered unresectable (as defined in Section 1.2)
- Recurrent lesions will be considered eligible if additional inclusion criteria are met.
- No immunosuppression
- Not a site of previous radiation therapy or chronic significant inflammation
- Fast growing lesions (doubling in size over a 4 week period of time) will be included if they are clinically suggestive of cSCC of the keratoacanthoma type.
- Well or moderately differentiated tumor as confirmed by skin biopsy
- Depth less than 2 mm (for non KA type cSCC)
- No perineural or vascular involvement in preliminary biopsy.
- d. Partial biopsy of squamous cell skin cancer identified as a target lesion(s) to determine the histological differentiation of the tumor or other adverse histological features
- e. In patients with multiple lesions, up to 3 lesions in a similar anatomical site, (trunk, limbs etc) that is at least 10 cm apart can be selected.
- f. Maximum of 5 lesions per patient can be selected for treatment
- g. Adequate organ function determined within 28 days prior to enrollment, defined as follows:
- h. Hematology:
- Absolute neutrophil count \geq 1500/mm3 (1.5x109/L)
- Platelet count ≥ 75,000/mm3 (7.5x109/L)
- Hemoglobin \geq 8 g/dL (without need for hematopoietic growth factor or transfusion support)
- i. Renal
- Serum creatinine ≤ 1.5 x upper limit of normal (ULN), OR 24-hour creatinine clearance ≥ 60 mL/min for subject with creatinine levels > 1.5 x ULN. (Note: Creatinine clearance need not be determined if the baseline serum creatinine is within normal limits. Creatinine clearance should be determined per institutional standard)
- j. Hepatic
- Serum bilirubin $\leq 1.5 \text{ x ULN}$
- Aspartate aminotransferase (AST) \leq 2.5 x ULN

- Alanine aminotransferase (ALT) \leq 2.5 x ULN
- k. Coagulation
- International normalization ratio (INR) or prothrombin time (PT) ≤ 1.5 x ULN, unless the subject is receiving anticoagulant therapy, in which case PT and partial thromboplastin time (PTT)/ activated PTT (aPTT) must be within therapeutic range of intended use of anticoagulants.

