9.0 STUDY PROCEDURES

9.1 Screening- Visit 0

Potential subjects will enter the screening period of the study after a completely executed informed consent has been obtained.

- Review of inclusion/exclusion criteria
- Medical and medication history and dermatological history review
- Skin check by the study provider
- Urine pregnancy test (72 hours before enrollment)
- Screening blood work to include a complete blood count (CBC), comprehensive metabolic panel (CMP) and pregnancy test (hCG) if urine pregnancy test comes back positive or inconclusive
- Identification of the target lesions for the study. One subject can have up to 5 TILs. One to three TILs may be on the same anatomical area but will need to be 10 cm apart. Up to 10 TNILs can be followed with no more than 2 TNILs selected in the same anatomical area as a TIL.
- Photographing and measuring of the target lesions
- Biopsy of any suspected non-target skin cancers (ie BCC). If a non-SCC skin cancer is confirmed the corresponding treatment should be completed prior to initiation of study intervention.
- Partial biopsy of lesions suspicious for cSCC (both TILs and TNILs) that have not already been biopsied. A partial shave or small punch biopsy may be done to sample the tissue.
- Vital signs obtained to include blood pressure, pulse, temperature, height and weight
- Ultrasound of TILs at Radiology Department for baseline evaluation (Appendix B)
- Assign screening number starting with the 2-digit site number followed by SCC

and a 3-digit sequential number, starting with -001 and increasing by one for each subject. If a subject fails the screening visit they may be replaced by an additional subject.

9.2 Enrollment- Visit 1

• See 9.3 for enrollment visit details

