9.4.3 Chart Review: Frequency of Nonmelanoma Skin Cancers (NMSCs)

Participants' charts will be reviewed to assess the number of nonmelanoma skin cancers before and after the intervention. The frequency of NMSCs before the intervention will include the 12 months before Visit 1 and the 24 months before Visit 1 if available. The frequency of NMSCs after the intervention will include the 12 months after the last injection visit (or Visit 4) and then 24 months after the last injection (or Visit 4) if available. This exploratory objective is an effort to quantify the abscopal effect those participants may experience.

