16.1.3 Exploratory Endpoint

The exploratory endpoint is to quantify the abscopal effect experienced by participants after their injections. Participants' charts will be reviewed to assess the number of nonmelanoma skin cancers before and after the intervention. The frequency of NMSCs before the intervention will include the 12 month and 24 month period before the first injection visit (or Visit 1). The frequency of NMSCs after the intervention will include the 12 months after the last injection visit (or Visit 4) and then 24 months after the last injection (or Visit 4) if available.

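### The abscopal analysis applies an unpaired test to paired counts, sets 24 months before against 12 months after without scaling, and has no rule for counting the enrolling tumours

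*Combined protocol and SAP*

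**What the plan says.** The analysis sentence in section 16.2.8 takes "the number of non-melanoma skin cancers in the 12 month and 24 month period prior to the TVEC injections" and continues "versus the number in the 12 months after the TVEC injections will be performed using the Wilcoxon Rank Sum Test". The same section also plans descriptive summaries.

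The source of the counts is in section 16.1.3: the participants' "charts will be reviewed to assess the number of nonmelanoma skin cancers before and after the intervention". Section 2.1 makes the trial single-arm, so each subject supplies both a before and an after count and there is no other group.

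The windows are in sections 9.4.3 and 16.1.3. 'Before' runs for 12 and for 24 months up to Visit 1. 'After' runs for 12 months from Visit 4, and then "24 months after the last injection (or Visit 4) if available". The test in section 16.2.8 does not use that 24-month after count.

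Entry (section 6.1) requires at least one histologically confirmed low-risk cSCC. Section 9.1 lists for Visit 0 "Partial biopsy of lesions suspicious for cSCC (both TILs and TNILs) that have not already been biopsied", together with a skin check and biopsy of suspected non-target cancers. Visit 1 follows one to four weeks later (section 2.4). No section says whether injected lesions (TILs), non-injected target lesions (TNILs) or other cancers found at screening are included in the before count.

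**The concern.** The three faults do not act in the same direction.

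1. **Pairing.** A subject who forms many skin cancers does so before and after treatment, so the two counts are positively correlated. The rank-sum test ignores this and measures the change against the spread between subjects. It does not create a false fall; it hides a true one.
2. **Exposure time.** At a constant rate, a 24-month count is expected to be twice a 12-month count. A significant fall in that comparison is therefore no evidence of an abscopal effect. The 12-against-12 comparison is free of this fault.
3. **Enrolling tumours.** Every subject has at least one biopsied cSCC just before Visit 1, and no comparable event is guaranteed after Visit 4. If those tumours are counted, as the window definitions imply, both comparisons lean towards a fall.

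Section 4.1 hypothesises a systemic anti-tumour response, so a small p-value here could be cited as support for it.

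**Working it through.** **Inputs from the documents.** n = 20 (section 2.3; 7 + 13 in section 16.2.1). Windows and test as in section 16.2.8. The plan gives no power, alpha or effect size for this analysis, so there is no stated figure to reproduce.

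**Assumptions.** The documents give no background rate. Subject rates λ are gamma with shape 1.5 and mean μ = 1, 2 or 4 cancers per year. Given λ, before ~ Poisson(λ·T_b) and after ~ Poisson(λ·θ·T_a), with T in years, θ = 1 for no effect and θ = 0.5 for a halving. Tests are two-sided at 5% with normal-approximation p-values. There were 4,000 simulated trials per cell (2,500 where index tumours are excluded), so the simulation standard error is at most √(0.25/4000) = 0.8 points (1.0 point for 2,500).

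**Step 1: pairing, 12 against 12 months.** With no effect, the variance of each count is μ + μ²/1.5 and the covariance is μ²/1.5. The within-subject correlation is therefore μ/(μ + 1.5) = 0.40, 0.57, 0.73 for μ = 1, 2, 4. An unpaired test treats it as zero.

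| 12 v 12 | μ = 1 | μ = 2 | μ = 4 |
|---|---|---|---|
| No effect, false fall, rank-sum | 0.8% | 0.3% | 0.1% |
| No effect, false fall, signed-rank | 2.2% | 2.7% | 2.4% |
| Halving, power, rank-sum | 23% | 33% | 46% |
| Halving, power, signed-rank | 37% | 65% | 88% |

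The nominal one-sided rate is 2.5%, so rank-sum is far too conservative. An extreme illustration: 20 subjects with 1 to 20 cancers before, and each exactly one fewer after, give p = 0.61 by rank-sum and p < 0.0001 by signed-rank.

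**Step 2: unequal windows.** With no effect, expected before/after = (λ × 2)/(λ × 1) = 2, whatever λ is.

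| No effect | μ = 1 | μ = 2 | μ = 4 |
|---|---|---|---|
| 24 v 12 raw, false fall, rank-sum | 33% | 46% | 59% |
| 24 v 12 raw, false fall, signed-rank | 63% | 89% | 99% |
| 24 v 12 annualised, signed-rank, two-sided size | 4.6% | 4.2% | 5.0% |
| 24 v 24, signed-rank, two-sided size | 4.9% | 4.4% | 4.5% |

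The paired test alone makes the false fall more likely, because it detects the exposure difference better. Equal windows or annualised rates restore the nominal size.

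**Step 3: enrolling tumours, 12 v 12, no effect.** In model A the index tumour adds one to the background count. In model B it is one of the subject's ordinary counts (only subjects with at least one cancer in the prior 12 months enter).

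| No effect | μ = 1 | μ = 2 | μ = 4 |
|---|---|---|---|
| A, counted, false fall, rank-sum | 88% | 43% | 8% |
| A, counted, false fall, signed-rank | 87% | 60% | 38% |
| A, excluded, false fall, signed-rank | 2.4% | 2.1% | 2.6% |
| B, counted, false fall, rank-sum | 38% | 5% | 0.3% |
| B, counted, false fall, signed-rank | 35% | 12% | 5% |
| B, one excluded, false *rise*, signed-rank | 28% | 26% | 23% |

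Neither counting rule is safe under both models.

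**Step 4: sensitivity.** A separate run used means of 2, 3 and 4 and gamma shapes 1 and 2, counting two-sided rejections. Power for a halving was 21–60% (rank-sum) and 61–91% (signed-rank). False rejection for 24 v 12 raw was 28–75% and 87–99%. Annualised signed-rank rejected in 4.6–5.5%. The directions were the same throughout.

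**The case against.** The strongest reply concerns weight. The analysis is exploratory, carries no alpha or decision rule, and is accompanied by descriptive summaries. The unpaired test errs on the conservative side. That limits the consequences, but section 16.2.8 still prespecifies a formal test that is wrong for the data.

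Sections 1.3, 3.3, 9.4.3 and 16.1.3 speak of frequency, which could mean a rate. They also list a 24-month after count, so like-for-like windows may have been intended. However, frequency is never defined as a rate, and the analysis section says number and omits the 24-month after count. A drafting slip is possible; the text as it stands still needs correcting.

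The third part draws the fairest criticism. Later study visits examine target lesions only (section 9.3), but the counts come from charts, and section 22 leaves standard-of-care assessments in the medical record. A drop in detection after treatment is therefore possible but not shown. The medication restrictions in section 7.4 may push the other way. Systemic agents may resume only after Visit 8, which is 4 + 4 + 6 + 14 = 28 weeks after Visit 4, or 28/52 = 54% of the 12-month after window. The topical ban covers only the study site. So the net direction is uncertain, and the size depends on unknown rates.

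It is also true that, with index tumours counted under model A, signed-rank gives more false falls than rank-sum at 2 and 4 cancers per year (60% and 38%, against 43% and 8%). The paired test does not cure the counting problem, which needs its own rule.

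**Conclusion.** The concern holds. On the test and on the windows the plan is wrong as written. Neither conclusion depends on an assumed rate: the counts are paired, and 24 months is twice 12. Only the sizes depend on the assumptions (20 subjects, 1 to 4 cancers per year, gamma heterogeneity). For 12 v 12, the unpaired test cuts power for a halving from 37–88% to 23–46%. For 24 v 12, a false significant fall occurs in 33–59% of trials, so that result cannot be read either way.

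On the enrolling tumours the plan is silent. The silence matters, but its effect ranges from under 1% to 88% false falls with the planned test, and the direction is not settled once other influences are allowed for. This is the least certain part, and the other two do not rest on it.

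The point should be fixed before the chart data are analysed. It does not touch the primary response-rate decision.

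**What to change.** Amend section 16.2.8 in one step:

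- Replace the rank-sum test with the Wilcoxon signed-rank test on within-subject differences, and report the paired median difference with a confidence interval.
- In the same change, compare equal windows only (12 v 12 months, and 24 v 24 where both are available), or annualised rates. The test must not be changed without this.
- State the counting rule, and report the comparison both with and without TILs, TNILs and cancers biopsied at Visit 0. Present the two results together, since each can mislead alone.

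The start of the after window can stay at Visit 4.

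The cost is SAP wording plus marking each before cancer in the chart data as TIL, TNIL, Visit 0 biopsy or other. No visits, subjects or procedures are added. The drawbacks are a little lesion-level classification, two results to report instead of one, and probably a smaller apparent before/after difference.

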16.3 Interim Analysis

In the first stage, the data will be evaluated in an ongoing manner and the investigators will be notified by the biostatistics team when: a. five subjects have demonstrated ORR or b. a total of 7 subjects have been recruited and \leq 4 of them demonstrate ORR.

17. ANALYSIS

- 17.1 Safety Analysis -see #16
- **17.2 Efficacy Analysis** –see #16
- 17.3 Interim Analysis see #16

18. **REGULATORY OBLIGATIONS**

18.1 Informed Consent

Before a subject's participation in the clinical study, the investigator or identified designee is responsible for obtaining written informed consent from the subject or legally authorized representative after adequate explanation of the aims, methods, anticipated benefits, and potential hazards of the study and before any protocol specified procedures, investigational product, intervention or device are administered or initiated.

18.2 Institutional Review Board

A copy of the protocol, proposed ICF, and all other applicable subject information will be submitted to the IRB for written approval. A copy of the written approval of the protocol and ICF must be on file at the institution before recruitment of subjects into the study.

The investigator is responsible for obtaining IRB approval/renewal at least annually throughout the duration of the study. Copies of the investigator's reports and the IRB continuance of approval must be on file at the institution.

The investigator must submit study information to the IRB as required by all applicable guidelines and requirements. The investigator will obtain IRB approval for subsequent protocol amendments; except changes to eliminate an immediate hazard to study subjects, and changes to the informed consent document from the IRB prior to implementation.

The investigator will notify the IRB of deviations from the protocol or serious adverse events occurring at the site and other serious adverse event reports occurring at or received from participating centers as applicable for multi-center trials following the IRB policies and procedures.

19. ADMINISTRATIVE PROCEDURES

19.1 Investigator Responsibilities

The PI will conduct this study in accordance with the current International Conference on Harmonization (ICH) guidance, the Good Clinical Practice (GCP) guidance, the Declaration of Helsinki, FDA regulations, local IRB and legal requirements.

19.2 Data and Safety Monitoring Board Protocol Review

Initial DSMB protocol review will be conducted prior to SRC and IRB submissions.

Any protocol revision or amendment that includes a potential change to any section of data and safety monitoring plan must be reviewed and approved by the DSMB *prior to* **the protocol amendment submission to the IRB**.

19.3 Multicenter Trials- Does not apply to this study

19.3.1 UACC DSMB and QA/QC Monitoring

19.3.2 Alternate DSMB Oversight

20. SUBJECT CONFIDENTIALITY

The principal investigator will ensure that the subject's confidentiality is maintained in compliance with Federal regulations, the International Conference on Harmonization (ICH), and Good Clinical Practice (GCP) Guidelines.

Oversight entities and/or regulatory authorities will be permitted direct access to review the subject's original medical records, electronic medical records or certified copies for verification of study-related procedures and data. Direct access includes examining, analyzing, verifying, and reproducing any records and reports that are important to the evaluation of the study.

21. STUDY DOCUMENTATION AND ARCHIVE

The investigator will maintain a list of appropriately qualified persons to whom he/she has delegated study duties. All persons authorized to make entries and/or corrections on CRFs will be included on the Delegation of Responsibilities Form.

Source documents, data, and records from which the subject's CRF data are obtained include, but are not limited to, hospital records, clinical/office/research charts, laboratory and pharmacy records, diaries, microfiches, radiographs, and correspondence. Source data will include information necessary for the reconstruction and evaluation of the trial.

The principal investigator or sponsor-investigator is responsible for maintaining a comprehensive and centralized filing system of all study-related (essential) documentation as required per ICH Guidelines. This can be accomplished by the PI, through the site's standard operating procedures and/or the institutions infrastructure.

The investigator will follow ICH Good Clinical Practice Guidelines and the Code of Federal Regulations for records and record retention.

22. DATA

Applicable data as specified as required in the protocol will be reported/submitted in the case report form (CRF). Data reported in the case report forms that are derived from source documents must be consistent with the source documents or the discrepancies must be explained. **CRFs will be completed via the UACC OnCore.**

Additional procedures and assessments may be performed as the institution's standard of care; however these data should remain in the medical records and should not be provided as part of the clinical study data unless it pertains to a serious adverse event.

The investigator is required to prepare and maintain adequate and accurate case histories that record all observations and other data pertinent to the investigation on each individual administered the investigational product/intervention/device, or employed as a control in the investigation.

23. PROTOCOL DEVIATIONS

The investigator will conduct the study in conformance with this protocol, generally accepted standards of Good Clinical Practice and all applicable federal, state and local laws, rules, and regulations.

Approvals or waivers for protocol deviations will be obtained from the sponsorinvestigator *prior to* occurring, except changes to eliminate an immediate hazard to study subjects. If immediate verbal approval is obtained, it will be documented by the research staff obtaining the approval and followed by a written protocol deviation form per the site standard operating procedures. The sponsor or the sponsor-investigator will sign the Protocol Deviation (Waiver) Approval Form or other similar document. The original will be filed in the regulatory binder and a copy will be placed in the subject's research file.

24. ECOG- does not apply to this study

25. COMMON TOXICITY CRITERIA (CTCAE)

CTCAE Version 4 will be used as reference to document AEs that occur in the study.

26. STUDY SCHEDULE

Test or Procedure	Screening Visit 0	Treatment Visit 1	Treatment Visit 2	Treatment Visit 3	Treatment Visit 4	Follow-up 1- Visit 5	Follow-up 2 Visit 6	Follow-up 3 Visit 7	Follow- up 4 Visit 8	Telephone Follow-up	Early Term Visit
Informed consent	Х										
Medical history ¹	Х										
Concurrent meds	Х	Х	Х	Х	Х	Х	Х	Х	Х		х
Vital Signs	Х	Х	Х	Х	Х	Х	Х	Х	Х		Х
Physical Exam	Х										
Hematology ²	Х			Х							Х
Serum chemistry ³	Х			Х							х
Urine or serum pregnancy test	х										
Tumor evaluation ⁴	Х	Х	Х	Х	Х	Х	Х	Х	Х		х
Tumor Ultrasound after visit ⁵	х						х				
Skin biopsy	Х										
Adverse event evaluation ⁶		Х	Х	Х	Х	Х	Х	Х	Х		х
IPTreatment Intervention Device (syringe)		Х	Х	Х	Х						
Telephone Assessment ⁷										X	

1 = Complete medical history will include demographics

2 = Hematology to include CBC, differential and platelet count

3 = Chemistry to include chemistries, liver function tests

4 = Tumor measurements, photographs

5 = Tumor ultrasound will only be performed for patients enrolled at UACC

6 = AE recording will begin on Visit 1 of the IP treatment/intervention/device

7 = Verbal assessment of changes of target lesions

27. GLOSSARY - Not applicable

28. DEFINITIONS- Not applicable

29. **REFERENCES**

5. Jesitus J. Lower-leg wound healing requires creativity, skill. Dermatology Times [Internet]. 2011 [cited 2017. Available from:

http://dermatologytimes.modernmedicine.com/dermatology-

times/news/modernmedicine/modern-medicine-feature-articles/lower-leg-woundhealing-requi

30. APPENDICES

30.1 Appendix A- Measurement of Lesions and Digital Photography

Digital Photographic Guidelines for Serial Photographic Documentation of cSCC Location and selected target lesions (TILs and TNILs)

• ID card with subject number, date and visit: two each

- Close-up view with millimeter scale of the target area of the selected cSCC: two each
- Global view of the target cSCC lesions area: two each

Equipment

Camera: Nikon Coolpix L127 with 16mp.

Procedures

In these clinical photographs for the duration of the study, the only variable allowed to change is the skin condition itself. Therefore, anything extraneous to the condition (furniture, etc.) is to be eliminated from the photographic field, starting at the entry visit through the final visit. The necessity of good end-of-study photographs should be stressed to patients to ensure their cooperation. Lighting, framing, and exposure must be held constant. In the end, the images should read like a time-lapse movie.

